### **Multicenter Studies**

As stated in the protocol, centers with less than 20 subjects will be pooled with larger centers within the same geographic region; this ensures centers are of a reasonable size for the purpose of the statistical analyses. This process will be performed and finalized before the treatment codes are unblinded.

### **Examination of Subgroups**

The rate of new stroke (ischemic or hemorrhagic) and clinical vascular event (ischemic stroke, hemorrhagic stroke, MI, vascular death) at 90 days will be presented for each level of the covariates listed previously. The extent to which the treatment effect varies across levels of each subgroup will be assessed through interaction tests.

### **Multiple Comparisons and Multiplicity**

A single primary efficacy variable has been defined for this study, with all other efficacy variables identified as secondary or other. Similarly only one treatment comparison is of interest in the study and therefore there are no requirements to adjust for multiple comparisons or multiple endpoints within this study.

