## Study Objective(s) and Endpoint(s)

### Study Objective(s)

The primary objective of this study is to assess the effects of a 3-month regimen of clopidogrel initiated with a loading dose of 300 mg followed by 75 mg/day combined with aspirin 75 mg/day during the first 21 Days versus a 3-month regimen of aspirin 75 mg/day alone on reducing the 3-month risk of any stroke (both ischemic and hemorrhagic) when initiated within 24 hours of symptom onset in high-risk patients with TIA or minor ischemic stroke.

The secondary objectives of this study are:

- To assess the secondary composite outcome: composite of any stroke, myocardial infarction, and vascular death
- To assess separately the effects of this Clopidogrel regimen versus ASA alone on the incidence of: new clinical vascular events (ischemic stroke/ hemorrhagic stroke/ TIA/ MI/ vascular death) as a cluster and evaluated individually.
- To assess whether there are differential treatment effects in predefined subgroups:
  - ✧ (<65 years vs ≥65 years)
  - ✧ Sex (male vs female)
  - ✧ Index event (minor stroke vs TIA)
  - ✧ TIA risk stratification ( $ABCD^2=4$  vs  $ABCD^2>4$ )
  - ✧ Previous stroke
  - ✧ Previous TIA
  - ✧ History of hypertension
  - ✧ History of diabetes
  - ✧ Systolic blood pressure at baseline (<140mmHg vs ≥140mmHg)
  - ✧ Time to randomization (<12 hours vs ≥12 hours)
  - ✧ Aspirin taken within 24h
- To assess the primary outcome measure in a Per-protocol (PP) population. This will include all patients who have not had a significant interruption of study drug (less than a total of 10 days off study drug) or major protocol violation.

Other objectives are:

- To evaluate treatment differences if changes in modified Rankin Scale from baseline to the last follow-up.
- To compare the safety of the two treatment regimens in terms of:
  - ✧ Severe or moderate bleeding (GUSTO definition)
  - ✧ Intracranial hemorrhage
  - ✧ Total mortality
  - ✧ AEs/SAEs

- In further exploratory analysis, to evaluate treatment differences of impairment (change in NIHSS scores), and Quality of Life (EuroQol EQ-5D scale) among survivors.

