## **General considerations for data analyses**

All programming will be performed using SAS Version 9.0. All analysis output will use the following treatment group naming conventions and treatment order:  
clopidogrel /ASA for a loading dose of clopidogrel 300mg followed by clopidogrel 75 mg /day day 2-90 plus blinded aspirin 75 mg once /day day 2-21 and then aspirin placebo day 22-90  
ASA for clopidogrel placebo on day 1, followed by aspirin 75 mg/day plus clopidogrel placebo day 2-90  
Unless otherwise specified all significance tests will be 2-sided at the  $\alpha=0.05$  level and all confidence intervals will be 95%.

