#### **Interactions with Subgroups**

Summary tables will be produced for the predefined subgroups and interactions between treatment and these subgroups will be investigated, using a Cox proportional hazard model, with pooled study center as a random effect. A separate model will be used for each interaction to determine its significance.

This will also be presented graphically on a tree plot.

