### Secondary Efficacy Analyses

#### **Rate of combined vascular events during the 3-month treatment period**

The rate of combined vascular events occurring during the treatment will be analyzed using a Cox proportional hazard model similar to that in the previous section, with the pooled study center as a random effect. A combined vascular event was defined as any of the 4 following events: ischemic stroke, hemorrhagic stroke, myocardial infarction, or death from cardiovascular causes. This will also be presented graphically on a Kaplan-Meier plot.

Each of the 4 vascular events will also be analyzed using the same method and the event rate for each event will be calculated for each treatment group.

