#### **Death from any causes**

The rate of overall death for any cause will be analyzed using a Cox proportional hazard model similar to that in the previous section, with the pooled study center as a random effect. The death rate will be calculated for each treatment group.

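### The SAP's no-adjustment statement is right for the primary test but is extended to six secondary outcomes and at least 11 subgroup interactions, all tested at 5% with no testing order and no nominal label

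*Supplement*

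**What the plan says.** The final SAP, under Multiple Comparisons and Multiplicity, starts from the tiers: "A single primary efficacy variable has been defined for this study, with all other efficacy variables identified as secondary or other". It adds that only one treatment comparison is of interest and concludes that "therefore there are no requirements to adjust for multiple comparisons or multiple endpoints within this study".

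The decision rule is the same throughout. General considerations for data analyses begins "Unless otherwise specified all significance tests will be 2-sided at the" and gives 0.05 as the level. The opening of Efficacy Analyses repeats 5% two-sided for main effects, and section 10.2.1 of the final protocol treats p below 0.05 as significant for all statistics.

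The tests beyond the primary are these:
- **Secondary outcomes.** Secondary Efficacy Analyses gives the combined vascular event a Cox model and then says "Each of the 4 vascular events will also be analyzed using the same method". The next paragraph adds "The rate of overall death for any cause will be analyzed using a Cox proportional hazard model". That makes six.
- **Subgroups.** Study Objective(s) lists, as a secondary objective, "To assess whether there are differential treatment effects in predefined subgroups", followed by 11 factors. Examination of Subgroups says "The extent to which the treatment effect varies across levels of each subgroup will be assessed through interaction tests". Interactions with Subgroups says "A separate model will be used for each interaction to determine its significance".

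The SAP uses the word exploratory only for the NIHSS and EQ-5D analyses.

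**The concern.** Having one primary variable and one comparison protects the primary test. It says nothing about the error rate of the other tests. The SAP nevertheless draws a conclusion about the whole study, and then makes a verdict on significance the stated purpose of each interaction model. This is a written rule, not an omission. Someone following it could call a secondary outcome or a subgroup difference significant at p below 0.05, even with a failed primary, and cite the SAP in support.

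What is at stake is the reading of the secondary and subgroup results. A chance interaction by age, sex or index event could be taken as a reason to narrow or widen the population to which the result applies. A chance finding on death or MI could be read as an established benefit or harm.

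**Working it through.** **1. The plan's own figure.** The documents state no error rate for the secondary or subgroup tests. The nearest stated figure is the sample size, which shows where the 5% is spent. Inputs, from protocol 10.1.1 and the SAP's Sample Size Considerations: control risk 0.14, relative risk 0.78 (so 0.14 × 0.78 = 0.1092), two-sided alpha 0.05, power 90%, 1:1 allocation.

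n per arm = [1.960 × √(2 × 0.1246 × 0.8754) + 1.282 × √(0.14 × 0.86 + 0.1092 × 0.8908)]² / 0.0308² = 2,415 (rounded up)

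The total is 4,830, and × 1.05 gives 5,072, as in protocol Table 2; the plan rounds to 5,100. The whole 0.05 belongs to the primary comparison.

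**2. Count of tests.**
- Secondary outcomes: composite, ischemic stroke, hemorrhagic stroke, MI, cardiovascular death, all-cause death = 6.
- Subgroup factors: age, sex, index event, ABCD2, previous stroke, previous TIA, hypertension, diabetes, systolic pressure, time to randomization, aspirin within 24 h = 11.
- Pooled: 6 + 11 = 17. If interactions are tested on both stroke and the clinical vascular event: 11 × 2 = 22, and 6 + 22 = 28.

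The count leaves out TIA, the per-protocol analysis, the t-tests on mRS, NIHSS and EQ-5D, and the Fisher tests on adverse events.

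**3. Chance of at least one false significant result under the global null.** If the tests are independent, this is 1 − 0.95^k. The right-hand column comes from 4,000 simulated null trials of 5,100 patients.

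| Tests | k | Independent | Simulated |
|---|---|---|---|
| Six secondary outcomes | 6 | 26.5% | about 20% |
| Interactions, stroke only | 11 | 43.1% | about 42% |
| Secondary + stroke interactions | 17 | 58.2% | about 53% |
| Interactions, both endpoints | 22 | 67.6% | about 48% |
| Secondary + both endpoints | 28 | 76.2% | about 58% |

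The documents do not give the simulation inputs, so these are assumptions: ischemic stroke 11.5%, hemorrhagic stroke 0.4%, MI 0.3%, cardiovascular death 0.3% plus 3% of stroke patients, other death 0.3%, and independent binary subgroup factors with prevalences from 3% to 70%. Tests on proportions and log odds ratios stood in for the Cox models. The primary test rejected in 5.15% of these trials, as it should.

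**4. Sensitivity to correlation.** With equally correlated normal test statistics:

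| Correlation | 0 | 0.3 | 0.5 | 0.8 |
|---|---|---|---|---|
| 6 tests | 0.265 | 0.242 | 0.207 | 0.139 |
| 11 tests | 0.431 | 0.374 | 0.305 | 0.180 |

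The expected number of false stroke interactions is 11 × 0.05 = 0.55 whatever the correlation.

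**The case against.** The strongest defence is that the statement is correct for the confirmatory question: one primary variable, one comparison, no interim analysis. The SAP does tier its endpoints, names its subgroups in advance and uses interaction tests rather than separate tests within subgroups. Reporting unadjusted secondary p-values beneath a single primary is common practice, and nothing in the documents ties a secondary or subgroup p-value to a treatment recommendation.

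Most of this stands, and it limits the point. The primary conclusion is safe, and the harm described is a risk of misreading, not a planned claim. The convention works, however, when the plan says that such p-values are descriptive. This plan says instead that no adjustment is required within the study, and it asks each interaction model for a significance verdict.

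A reader might go further than the documents allow in three ways:
- **That there is no hierarchy at all.** There are tiers. What is missing is an order or a gate within the secondary tier.
- **That a false finding is likely in each family.** Only the pooled sets pass 50% in the simulation; the six secondary outcomes alone do not come near it.
- **That 22 interaction tests are planned.** Examination of Subgroups presents two endpoints by subgroup but does not name the endpoint for the interaction tests, and the modelling rule sits under the primary analysis. Twenty-two is one reading; 11 is the safe count.

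**Conclusion.** The point holds for secondary and subgroup inference only. Under the global null, the plan as written gives about a 20% chance (26.5% at most, under independence) of at least one false significant secondary outcome. For 11 near-independent stroke interactions the chance is about 42 to 43%, falling to about 31% at correlation 0.5 and 18% at 0.8. For the 17 tests together it is about 53%. The simulated figures rest on assumed event risks and on independent subgroup factors; the closed-form figures assume independent tests. The primary type I error, the power and the sample size are not affected. The change should be made, but the trial's main result does not depend on it.

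**What to change.** In Multiple Comparisons and Multiplicity, limit the last sentence to the primary comparison and add:

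*The composite of stroke, MI and vascular death is tested at two-sided 0.05 only if the primary is significant. P-values for all other secondary and other efficacy outcomes and for all subgroup interactions are nominal and descriptive, reported with estimates and 95% CIs, and support no claim of significance.*

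In Interactions with Subgroups, give the purpose of each model as estimating the ratio of hazard ratios with its 95% CI, and state how many interaction tests are done and on which endpoint.

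Make the general 5% rules subject to this sentence, or they will contradict it: General considerations for data analyses, the opening of Efficacy Analyses, and protocol section 10.2.1. Leave the safety reporting of mortality as it is (Safety Endpoint; Deaths and Serious Adverse Events).

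The nominal label does most of the work. The composite is nearly all stroke, so under the assumed risks it is significant without the primary in only about 1% of null trials, and the gate alone would change little.

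The cost is wording, before unblinding; protocol section 10.1 foresees a final SAP before database lock and code breaking. No patients, data or models are added. The sponsor gives up formal significance claims for component outcomes and subgroups, and for the composite if the primary fails.

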## **Data handling conventions**

### **Premature Withdrawal and Missing Data**

If any subject withdraws prematurely from the study (prior to the final visit D90±7 days assessment), they are required to complete the withdrawal visit in the CRF. The reasons for withdrawal will be presented in a summary table. For the purposes of summaries and analysis of clinic visit data, this visit will be assigned to the next scheduled clinic visit for that subject, regardless of whether the date falls within the next visit window.

Subjects who withdraw before the end of the study, but who do provide at least one post-baseline measure for a particular endpoint, will be included in the analysis.

Subjects who do not attend any visits after randomization will be excluded from analysis of new stroke and clinical vascular event rates, and safety outcomes, as no post-baseline data will be available.

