#### 4.6.2 Secondary Efficacy Endpoint

- Percentage of composite of any stroke, myocardial infarction, and vascular death within 3 month.
- Patients with the 3-month new clinical vascular events (ischemic stroke/ hemorrhagic stroke/ TIA/ MI/ vascular death) evaluated individually.
- Modified Rankin Scale score changes (continuous) and dichotomized at percentage with score 0-2 vs. 3-6 at 3 month follow-up (Scale is described in Appendix 2).
- Further efficacy exploratory analysis:
  - ✧ Impairment (changes in NIHSS scores at 3 month follow-up), (Scale is described in Appendix 3).
  - ✧ Quality of Life (EuroQol EQ-5D scale, described in Appendix 4).
- Efficacy endpoint will also be analyzed stratified by etiological subtypes (non-ICAD vs. ICAD), by time randomization (< 12 hours vs. ≥ 12 hours), by qualifying event (TIA vs. minor stroke), and by age (<65 years vs. ≥65 years).

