### **7.5.3 Handling of patients after definitive treatment discontinuation**

Patients will be followed according to the study procedures as specified in this protocol up to the scheduled date of study completion, or up to recovery or stabilization of an AE, whichever comes last

All withdrawals should be recorded by the Investigator on the appropriate CRF pages when considered to be confirmed

All patients who have discontinued the study drug prior to the last visit should have a complete end-of-study visit at three months.

For patients considered lost to follow-up, the CRF must be completed up to the last visit performed. The Investigator should make every effort to contact the patient and to identify the reason why he/she failed to attend the visit and to determine his/her health status

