### **10.2.1 Primary Outcomes**

The primary analysis will be intention to treat, with inclusion determined by receipt of first study drug dose. Missing values will remain missing and patients will be censored at their last follow-up assessment (time of clinical event, end of study, or last visit prior to loss to follow-up). Time to randomization was presented with group mean. Differences between treatments in the risk of stroke (ischemic or hemorrhagic) event during maximum 90-day follow-up were assessed using standard Kaplan-Meier time-to-event approaches, and the hazards ratios with 95% CI were reported. The time to the first event was used in the model when there were multiple events of the same type. This approach is being taken to maximize the time dependent information in the trial while still acknowledging the ease of interpretation of risks. All statistics will be two-sided with  $p < 0.05$  considered significant.

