### Other Efficacy Analyses

#### **Disability measure**

Changes of the modified Rankin Scale (mRS) between the end of study and baseline will be summarized for the two treatment groups among the survivors during the study. The treatment difference will be tested using student t-test.

---

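### The SAP files a study-withdrawal visit as the next scheduled visit whatever its date, so mRS and NIHSS scores taken weeks early can be analysed as Day 90

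*Supplement*

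**What the plan says.** The final SAP, under Premature Withdrawal and Missing Data, deals with subjects who leave the study before the Day 90±7 assessment. It says that "they are required to complete the withdrawal visit in the CRF". When visit-based results are summarised and analysed, the withdrawal assessment is "assigned to the next scheduled clinic visit for that subject, regardless of whether the date falls within the next visit window". The next paragraph keeps in the analysis subjects who withdraw but "who do provide at least one post-baseline measure for a particular endpoint, will be included in the analysis".

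The SAP's Disability measure section then states: "Changes of the modified Rankin Scale (mRS) between the end of study and baseline will be summarized". The arms are compared by t-test among survivors, and NIHSS change is handled in the same way under Neurological impairment.

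Final protocol 4.6.2 lists mRS change, and mRS "dichotomized at percentage with score 0-2 vs. 3-6 at 3 month follow-up", together with NIHSS change at 3 months. Protocol objective 3.2.4 and the SAP's Study Objectives instead place the mRS assessment at the last follow-up. The protocol's schedule (1.2), contact list (4.5) and procedures (9.1 to 9.4) provide for screening/Day 1, Day 21±2, Day 90±7 and event visits. They contain no withdrawal visit.

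**The concern.** Once the Day 21 visit is past, the next scheduled visit is always Day 90. The SAP rule removes any date limit, so it acts as an undeclared carry-forward: the early score is used, and it is also stored under a visit label that does not match when it was taken.

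A patient who leaves event-free in the fourth week contributes a favourable change score with most of follow-up unobserved. A patient who leaves shortly after a disabling event contributes a score taken before any recovery. If the two arms lose patients for different reasons, for example bleeding in one and recurrent ischaemia in the other, these errors need not cancel in the comparison of mean mRS and NIHSS change. The SAP offers no window-restricted or other sensitivity analysis. It also tabulates attendance at each clinic visit by arm; if that table follows the same assignment, Day 90 attendance will look more complete than it was.

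**Working it through.** **Visit windows** (protocol 9.2 and 9.3)
- Day 21±2: Day 19 to Day 23.
- Day 90±7: Day 83 to Day 97.

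**How early a relabelled score can be**
- Withdrawal visit on Day 24: the Day 21 window closed one day before, so the next visit is Day 90. Gap to the opening of the window: 83 − 24 = 59 days. Gap to Day 90: 90 − 24 = 66 days.
- Earliest case: Day 21 visit held on Day 19 and withdrawal visit on Day 20. Gaps: 83 − 20 = 63 days and 90 − 20 = 70 days.
- Latest case still outside the window: Day 82. Gaps: 83 − 82 = 1 day and 90 − 82 = 8 days.
- A genuine Day 90 score is at most 7 days from Day 90.

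A withdrawal visit before the Day 21 visit is filed as Day 21 and does not enter Day 90.

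**How many patients**

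The documents give no study-withdrawal rate. Number = 5,100 × assumed rate:

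| Assumed rate | Patients |
|---|---|
| 1% | 51 |
| 2% | 102 |
| 5% | 255 |
| 10% | 510 |

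At each assumed rate this is a ceiling, because only leavers who attend a withdrawal visit after the Day 21 visit and before Day 83 are relabelled as Day 90.

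**How far an arm's mean can move**

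Shift in an arm's mean = share relabelled × mean change in score between the withdrawal visit and Day 90. Assumed examples:
- 5% × 0.5 point = 0.025 point.
- 10% × 1 point = 0.10 point.

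The bias in the treatment comparison is the difference between the two arms' shifts. It is zero if share and mean change are the same in both arms, and it reaches the figures above only if one arm carries the whole effect.

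**Time point, side by side**
- Protocol 4.6.2: mRS and NIHSS at 3 months. A Day 24 score does not qualify.
- Protocol 3.2.4 and SAP Study Objectives: mRS at last follow-up. A Day 24 score from a leaver would qualify.
- SAP Other Efficacy: end of study against baseline, with the relabelling rule supplying the end-of-study value.

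The three cannot all describe one estimate when a patient leaves early.

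**The case against.** The strongest reply is that the SAP's own objective speaks of the last follow-up. For a patient who has left, the withdrawal visit is the last follow-up, so using that score may be intended. This stands in part: it shows that the time point is unsettled. It does not justify labelling the score Day 90, and it does not fit protocol 4.6.2. Early leaving is also disclosed elsewhere: the SAP reports completed and withdrawn numbers by arm, reasons for withdrawal, and time to withdrawal. That is a fair limit on the attendance point. Finally, treating out-of-window scores as missing can itself bias the result if leavers differ, so a sensitivity analysis has to go with the change.

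Four stronger readings are tempting and are not supported:
- *A direct contradiction with the protocol's missing-data rule.* "Missing values will remain missing" stands in protocol 10.2.1 on the primary outcome, in the same sentence as the censoring rule. Section 10.2.2 extends that strategy only to most secondary analyses, then gives NIHSS and mRS a separate regression with no missing-data rule.
- *Duplicate Day 90 records for patients who stop study drug.* Protocol 7.5.3 says: "All patients who have discontinued the study drug prior to the last visit should have a complete end-of-study visit at three months". Those patients remain in the study; the SAP rule concerns withdrawal from the study, so no second record follows.
- *Relabelled EQ-5D values.* The protocol collects EQ-5D only at Day 90, and nothing states that a withdrawal visit includes it.
- *255 patients affected.* The 5% in the sample-size section is an allowance for medication non-adherence. It is not a study-withdrawal rate.

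**Conclusion.** The point holds in a limited form. A stated SAP rule lets mRS and NIHSS scores from a withdrawal visit, between 8 and 70 days before Day 90, enter the analysis as Day 90 values, with no date limit and no sensitivity analysis. It does not fit the 3-month endpoints in protocol 4.6.2, and it depends on a visit that the protocol does not schedule.

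Its reach is narrow. The rule covers clinic visit data, so time to first stroke is unaffected. In the SAP these scales are other or exploratory endpoints; in the protocol mRS is a secondary endpoint. The SAP tests mean mRS change only, so an effect on the 0–2 versus 3–6 split would arise only if that protocol analysis were run on the relabelled data.

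The size cannot be established from the documents. The figures of 51 to 510 patients and of 0.025 to 0.10 point rest on assumed withdrawal rates and assumed score changes. The conclusion also assumes that mRS and NIHSS are recorded at the withdrawal visit, whose content neither document lists. The change should be made before unblinding, but the trial's main conclusion does not depend on it.

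**What to change.** 1. Replace the assignment sentence in the SAP: a score counts as Day 90 only if its actual date falls within Day 90±7.
2. Keep earlier withdrawal scores under their true date. Prespecify a sensitivity analysis for mRS and NIHSS change, for example multiple imputation with the early score as an auxiliary variable, plus a last-observation analysis named as such.
3. State one time point for mRS and NIHSS, and use it in protocol 3.2.4, protocol 4.6.2 and the SAP's objectives and endpoints.
4. Either add the withdrawal visit to the protocol schedule with a list of its assessments, or remove it from the SAP.
5. Base the visit-attendance table on actual visit dates.

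The cost is a few sentences and a date check in the programs. The downside is somewhat fewer Day 90 values in the main mRS and NIHSS analyses, with possible bias if leavers differ from those who stay; the sensitivity analysis in step 2 is there to show whether that matters.
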